5.1. Allocation to Treatment

The investigator's knowledge of the treatment should not influence the decision to enroll a particular subject or affect the order in which subjects are enrolled.

Investigators will use an Interactive Response Technology (IRT) to assign a unique subject identification number to each subject who has signed the informed consent document (ICD). This identifying number will be retained throughout the duration of the study participation. Subject eligibility for participation in the study will be determined following the Screening assessments (V1). Once the subject is determined to be eligible for treatment, the investigator will obtain a randomization number and study medication assignment utilizing the IRT.

Subjects, who received PF-02545920 20 mg BID in the preceding A8241021 study, will continue to receive PF-02545920 20 mg BID in this study. Subjects, who previously received either PF-02545920 5 mg BID or placebo in the A8241021 study, will be titrated to PF-02545920 20 mg. The titration will start at 5 mg BID and the dose will be increased by 5 mg BID every 7 days, up to a 20 mg BID to be reached at Day 22, and maintained until Month 12 (V8). Subjects will take 4 tablets twice a day provided in blister packs from Baseline Day 1 (V2) to Week 4 (V4) and in bottles from Week 4 (V4) to Month 12 (V8). For subjects, who have been de-escalated from 20 mg BID to lower dose in the preceding study A8241021, the investigator should contact the sponsor study clinician and medical monitor to discuss titration scheme.

Table 3. Allocation to Study Treatments

Treatment Group	Study Treatment	Drug Administration	Duration
20 mg PF-02545920, Subjects receiving 20 mg PF-02545920 in the preceding A8241021 study	Days 1-365 Four 5 mg tablets of PF-02545920	Orally, BID	12 months (Days 1-365)
20 mg PF-02545920, All other subjects	Days 1-7 One 5 mg tablet of PF-02545920 Three placebo tablets for PF-02545920 Days 8-14 Two 5 mg tablets of PF-02545920 Two placebo tablets for PF-02545920 Days 15-21 Three 5 mg tablets of PF-02545920 One placebo tablet for PF-02545920	Orally, BID	12 months (Days 1-365)
	Days 22-365 Four 5 mg tablets of PF-02545920		

5.2. Breaking the Blind

All subjects will receive 20 mg PF-02545920 BID starting on Day 22. The initial titration period between Day 1 and Day 22 will be double blind.

The method for breaking the blind will be an electronic process via IRT. At the initiation of the study, the study site will be instructed on the method for breaking the blind. Blinding codes should only be broken in emergency situations for reasons of subject safety. The responsibility to break the treatment code in emergency situations resides with the investigator. Whenever possible, it is requested the investigator or sub-investigator consult with a member of the study team prior to breaking the blind. When the blinding code is broken, the reason must be fully documented and entered on the case report form (CRF)/data collection tool (DCT) and the Sponsor is to be notified.

5.3. Subject Compliance

Dosing compliance is documented in the accountability logs, the electronic Case Report Form (eCRF) and in the subject's dosing diary. On Day 1 subjects will be instructed on how to take their medication each day, twice a day, during outpatient dosing days. A dosing diary will be given to the subject for the first four weeks, with instructions on how to record daily times of study drug administration. The subject will bring the used and in-use medication blister cards and/or bottles back to the clinic at each visit. At each visit, a tablet count will be done by the research staff, and the subject will be questioned about any missed or extra doses taken. Checking blister packs and bottles will allow the site personnel to check on administration compliance.

A subject may be considered non-compliant if they have missed more that 20% of the required doses since the first dose.

Medication Compliance Formula:

$$\% \ Compliance = \frac{Actual \ \# \ of \ Capsules \ Taken}{Total \ \# \ of \ Capsules \ Prescribed} \times 100$$

For example, if the subject is required to take 4 tablets twice daily for exactly 12 months (365 days, 2,920 tablets prescribed) but according to the amount of drug returned the subject took 2280 tablets of study medication, percent compliance is calculated as follows:

$$\frac{2280}{2920} \times 100 = 78\% Compliance$$

Dosing record from Baseline to Week 4 should contain details of missed or lost doses for accurate compliance measurement. Compliance will be assessed by pill count after Week 4. If compliance is less than 80% or greater than 120% at any visit, the reason(s) must be noted. Subjects should not make up for missed doses. Missed dose(s) related to AEs should be discussed with the sponsor.

5.4. Drug Supplies

The study medication will be as follows:

Table 4. Drug Supplies

Dosage Forms	Compounds	Appearance
Active drug tablet 5 mg	PF-02545920	White to off white small round tablets
Placebo tablets for 5 mg PF-02545920	Placebo	White to off white small round tablets

5.4.1. Dosage Form(s) and Packaging

PF-02545920 will be supplied by the sponsor as tablets containing 5 mg of active drug. For treatment between Baseline Day 1 (V2) and Week 4 (V4), drug supplies will be packaged in blister packs with labels containing morning and evening administration and titration instructions. The tablet count per blister pack will be appropriate for the dosing regimen and treatment period. The blister pack also allows for an accurate blind de-escalation with 5 mg decrement, should the Principal Investigator assess that a subject requires a (temporary or permanent) dose adjustment due to intolerable AE(s) (See Appendix 1). The blister card will have column labels for each tablet (A, B, C, D) to facilitate giving direction to the subject. Once AEs have resolved the PI will have the option to resume escalation.

For treatment between Week 4 (V4) and Month 12 (V8), drug supplies will be packaged in high-density polyethylene (HDPE) bottles.

Pfizer will provide all study medication except for concomitant and rescue medications.

5.4.2. Preparation and Dispensing

Only qualified personnel who are familiar with procedures that minimize undue exposure to them and to the environment should undertake the preparation, handling, and safe disposal of the study drug.

The study medication will be dispensed using a drug management system at each visit from V2 to V7. Dispensing will be done by a qualified staff member via unique container numbers in either blister cards or bottles, in quantities appropriate for the study visit schedule. The subject should be instructed to maintain the product in the blister cards or bottles throughout the course of dosing and return the blister cards and/or bottles to the site at the next study visit.

5.5. Administration

Subjects will be instructed to take the study medication twice a day (BID), morning and evening, at approximately the same time of day throughout the study, and if possible (ideally) at least one hour prior to, or two hours after meals. Subjects will swallow the study medication whole, and will not manipulate or chew the medication prior to swallowing. Drug will be dispensed to the subject at each clinic visit starting at Baseline Day 1 (V2) and ending with Month 9 (V7).

Between clinic visits, subjects will be responsible for establishing a process for reliable outpatient dosing to ensure dosing compliance. To facilitate safety monitoring during the titration phase, a dosing diary will be supplied to the subject for the first four weeks and subjects will be instructed to record the time of each daily dose of study medication. Subjects will be instructed to bring the completed diary to Week 2 and Week 4 Visits, along with used and in-use blister packs containing the study medication. The study staff will use bottles to assess compliance after the Week 4 Visit.

If a subject misses a scheduled morning dose, that dose should be taken as soon as possible, but not later than 6 hours beyond the scheduled time of administration. If it is greater than 6 hours beyond the scheduled dose, the subject should be instructed to skip that dose and resume dosing at the next regularly scheduled time. Missed doses and reasons for missed doses should be recorded on the dosing diary.

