1.2.4. Dose Selection Rationale

A single dose of 20 mg PF-02545920 (BID) will be studied to evaluate long-term safety and efficacy in subjects with HD. Based on the previous pre-clinical efficacy data and clinical safety data, a dose of 20 mg BID is estimated to produce the most robust PDE10A inhibition while still being well tolerated. The 20 mg BID dose is the maximum dose evaluated in the double blind Phase 2 Proof-Of-Concept Study (A8241021) in subjects with HD.

A titration scheme will be used for all subjects who did not receive the 20 mg BID dose in the previous study A8241021 in order to mitigate the potential risk of dystonia.

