3.1. Stopping Criteria

White Blood Count (WBC) and Neutrophil (ANC) Monitoring:

WBC counts and differentials will be reviewed at Screening (V1) and Baseline Day 1 (V2) reviewed and performed at the following visits: Week 2 (V3), Week 4 (V4), Month 3 (V5), Month 6 (V6), Month 9 (V7), Month 12 (V8)/ET and Follow-up (V9). In the event that the ANC and/or WBC results are abnormal, the investigator (or a delegate) will contact the subject to inquire about potential symptoms. The lab results will be reviewed by the investigator (or delegate) as soon as possible once they are available, but no later than 2 business days after receipt of the lab results. The investigator must confirm and document that the results do not meet WBC/ANC stopping criteria listed below and that the subject can

continue to receive study medication. The Pfizer Medical Monitor and the Pfizer clinician should be contacted immediately if a subject meets any of the WBC/ANC stopping criteria. A separate source document worksheet will be provided to each site to assist in the monitoring of these criteria. See Neutropenia Assessment for a description of the minimal safety assessment for evaluating cases of neutropenia meeting any of the study stopping criteria described below.

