3.1.1. Subject Stopping Criteria

- Subjects with WBC ≤3000 cells/mm³ but ≥2000 cells/mm³ and/or ANC ≤1500 cells/mm³ but ≥1000 cells/mm³ will have study treatment temporarily suspended and have three times per week WBC counts with differential until WBC ≥3000 cells/mm³ and ANC ≥1500 cells/mm³. Subjects who have at least 2 consecutive WBC or neutrophil findings meeting this criterion will be evaluated by a hematologist to determine the etiology of the adverse event and for medical management recommendations.
- Subjects will be discontinued from study participation if WBC ≤2000 cells/mm³ and/or ANC ≤1000 cells/mm³. Subjects who are discontinued or permanently suspended due to WBC or ANC findings will be evaluated by a hematologist to determine the etiology of the adverse event and for medical management recommendations.

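### The protocol has no rule for restarting after several days of missed doses, so by default a subject returns to untitrated 20 mg BID without calling the site

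*Protocol*

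**What the plan says.** **Missed doses.** Section 5.5 allows a missed morning dose to be taken up to 6 hours late; after that, "the subject should be instructed to skip that dose and resume dosing at the next regularly scheduled time". Section 5.3 adds that missed doses are not made up. Neither section sets a limit on consecutive missed doses.

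**Dose.** Table 3 (Section 5.1) gives four 5 mg tablets BID from Day 22 to Day 365 for everyone, and from Day 1 for subjects continuing from 20 mg.

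**Detection.** Tablets are counted and subjects questioned at each visit. "If compliance is less than 80% or greater than 120% at any visit, the reason(s) must be noted". For reporting missed doses as they occur, "a dosing diary will be supplied to the subject for the first four weeks". After Week 4, visits fall on Days 91, 182, 273 and 365.

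**Contact with the sponsor.** It is required in specific cases:
- Adverse events (5.3): "Missed dose(s) related to AEs should be discussed with the sponsor".
- Low counts (3.1): "The Pfizer Medical Monitor and the Pfizer clinician should be contacted immediately if a subject meets any of the WBC/ANC stopping criteria". Under 3.1.1, subjects in the intermediate range "will have study treatment temporarily suspended and have three times per week WBC counts with differential until WBC" and ANC recover.
- A positive urine pregnancy test (7.7.5): drug is withheld and the sponsor notified.

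None of these states the dose at which treatment restarts.

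**Titration.** Section 1.2.4: "A titration scheme will be used for all subjects who did not receive the 20 mg BID dose in the previous study A8241021", with mitigation of dystonia as the reason. For subjects de-escalated from 20 mg BID in the preceding study, Section 5.1 says "the investigator should contact the sponsor study clinician and medical monitor to discuss titration scheme".

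**The concern.** The protocol treats the step from little or no drug to 20 mg BID as one that needs care. Entrants from placebo or 5 mg BID are titrated over 21 days, and the scheme is discussed with the sponsor even for a subject who had only been reduced below 20 mg. A subject who has taken nothing for several days may have less drug on board than either the 5 mg entrant or the de-escalated one, yet has neither safeguard.

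This is more than a detail that the site could fill in by judgement. The restart happens at home, between visits about three months apart, and nothing prompts the subject to call first. The site learns of the gap, if at all, after the full dose has been resumed.

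At stake is avoidable exposure to a possible dystonia risk, in a study whose primary endpoint includes the frequency and severity of extrapyramidal events. Nor does any output described in the SAP identify an event as following a restart: SAP 8.3.4 covers temporary discontinuations due to adverse events.

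**Working it through.** **1. The plan's own figures.** The compliance example in 5.3: 2280/2920 = 78.1% (stated as 78%). Dystonia at titrated 15 mg Q12H in A8241012 (1.2.2): 6/74 = 8.1% (as stated). Both reproduce.

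**2. How much drug is left.** Section 1.2.3 gives a parent terminal half-life of 11-13 h. With first-order decay, the fraction left is 2^(-t / half-life).

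| Time since last dose | 11 h | 13 h |
|---|---|---|
| 24 h | 22.0% | 27.8% |
| 48 h | 4.9% | 7.7% |
| 72 h | 1.1% | 2.2% |

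Five half-lives are 55-65 h (2.3-2.7 days). A subject who restarts at 72 h has missed the doses at 12, 24, 36, 48 and 60 h, which is 5 doses.

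**3. How long a gap passes the 80% check.** Visit days come from the Schedule of Activities, with two doses a day. The longest run is floor(0.2 × doses), assuming no other missed doses and visits on their target days.

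| Interval | Days | Doses | Longest run | Compliance |
|---|---|---|---|---|
| Week 4 to Month 3 | 63 | 126 | 25 (12.5 days) | 101/126 = 80.2% |
| Month 3 to Month 6 | 91 | 182 | 36 (18 days) | 146/182 = 80.2% |
| Month 6 to Month 9 | 91 | 182 | 36 (18 days) | 146/182 = 80.2% |
| Month 9 to Month 12 | 92 | 184 | 36 (18 days) | 148/184 = 80.4% |

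One more missed dose between Months 3 and 6 gives 145/182 = 79.7% and triggers the note. Section 5.3 also speaks of doses missed since the first dose. Read cumulatively, the limit at Month 6 is floor(0.2 × 364) = 72 doses (36 days). A gap of 5 doses shows as 177/182 = 97.3%.

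**4. What the documents say about risk without titration.**
- 1.2.2: 43% untitrated against 8.1% titrated, at 15 mg Q12H, across two schizophrenia studies.
- 1.2.2, within A8241018: 14.2% with 7-day steps, against 33.4% and 25.0% with shorter steps.
- 1.2.2: 1 of 11 healthy subjects at a single 20 mg dose. In A8241002, 8 of 40 randomized subjects had dystonia, more often at 20 mg BID and above.
- Appendix 1: 1 of 24 subjects with schizophrenia (4.2%) at repeated untitrated 20 mg.

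These figures conflict, and all describe a first start rather than a restart. None comes from subjects with HD. They cannot be turned into an expected number of cases.

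**The case against.** **The text is silent; it does not order a return to 20 mg.** A reader might infer that the protocol directs a washed-out subject back to full dose. It does not: the rule in 5.5 concerns one late dose. De-escalation by 5 mg is available for intolerable adverse events, and Figure 2 leaves room for the investigator's judgement. That stands. Full dose is the default only because Table 3 and the bottles supply it and no one is called first.

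**Other duties to report.** Section 8.4 requires immediate notice of medication dosing errors, including doses taken at the wrong time and uses that the protocol does not foresee. It could be stretched to a gap, but it does not name omitted doses, would usually operate after the restart, and sets no dose.

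**The comparison groups differ.** Titrated entrants have not been on 20 mg in the preceding study. De-escalated subjects have probably shown intolerance, although that study's protocol is not available here. A subject who tolerated 20 mg and forgot doses matches neither. This also stands: that tolerance is lost on washout is an inference from plasma half-life.

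**Existing protection.** Appendix 1 provides telephone assessment, rescue anticholinergics, 24-hour follow-up and step-down, and 1.2.2 reports that dystonia generally responded to as-needed treatment. Entry also requires compliance in the preceding study. These limit the harm, but they do not prevent an untitrated restart.

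**The analysis.** A reader might infer that events after a restart would be wrongly counted against a steady 20 mg BID category. The SAP has no such category. All events from the first dose to 28 days after the last are treatment-emergent (SAP 6.2), and they are summarized overall and by previous treatment group (SAP 8.3.1). An event after self-interruption belongs in that summary. What remains is only that a restart cannot be identified from the outputs described, and the sponsor's reporting standards are not in the documents.

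**Conclusion.** The point holds as a gap in the dosing instructions, of minor rank. No section covers a multi-day interruption or states a restart dose. For gaps not caused by an adverse event, a laboratory suspension or a pregnancy-test hold, the plan does not expressly require contact before restarting. After 72 h the subject has 1.1-2.2% of parent drug left, and a run of up to 18 days between later visits does not trigger even a noted reason.

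This assumes that the half-life, reported in healthy subjects and subjects with schizophrenia, carries over to HD; that compliance is computed per visit interval; and that the missed doses fall in one run. How often such gaps occur, whether tolerance is lost, and the excess risk on restart cannot be determined from the documents. They therefore support a rule to call before restarting. They do not support the stronger step of compulsory re-titration for every subject at a fixed 72 h.

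**What to change.** Add to Section 5.5:

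> If about 3 days or more (5 or more consecutive doses) are missed for any reason, the subject must call the site before taking further study drug. The investigator contacts the sponsor study clinician and medical monitor to agree the restart dose, with the 5 mg BID weekly-step titration in Section 5.1 as the reference scheme. During the titration blister period (Days 1-21, titrating subjects) the restart is arranged through the sponsor or IRT.

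Cross-refer to this from 3.1.1 and 7.7.5, where treatment is also held with no restart dose. Record the interruption and restart dates in the eCRF so that extrapyramidal events after a restart can be identified.

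Only titrating subjects on Days 1-21 have packs that mix active and placebo tablets. Because that period is blinded, the site cannot tell who they are, so any call in those days should go by the sponsor or IRT route. From Day 22 every tablet is an active 5 mg tablet, and no new supply is needed.

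**Cost:** one paragraph, two cross-references and two dates.

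**Downsides:**
- An affected subject spends some time below 20 mg BID: at most 21 of 365 days (5.8%) per full re-titration.
- Stepping up at home from bottles, with no diary, invites dosing errors.
- The rule depends on the subject calling. A gap that is not reported is found only at the next visit.
- The threshold of roughly 72 h rests on plasma half-life alone.

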5.6. Drug Storage

The investigator, or an approved representative (eg, pharmacist), will ensure that all investigational products are stored in a secured area, with controlled access under recommended storage conditions (controlled room temperature between 15-25°C) and in accordance with applicable regulatory requirements.

Investigational product should be stored in its original packaging or container and in accordance with the drug label. Storage conditions stated in the SRSD (Investigator Brochure) will be superseded by the storage conditions stated on the labeling.

Site systems must be capable of measuring and documenting (for example, via a log), at a minimum, daily minimum and maximum temperatures for all site storage locations (as applicable, including frozen, refrigerated and/or room temperature products). This should be captured from the time of investigational product receipt throughout study. Even for continuous monitoring systems, a log or site procedure which ensures active daily evaluation for excursions should be available. The operation of the temperature monitoring device and storage unit (for example, refrigerator), as applicable, should be regularly inspected to ensure it is maintained in working order.

Any excursions from the product label storage conditions should be reported upon discovery. The site should actively pursue options for returning the product to labeled storage conditions, as soon as possible. Deviations from the storage requirements, including any actions taken, must be documented and reported to the sponsor.

Once an excursion is identified, the investigational product must be quarantined and not used until the sponsor provides documentation of permission to use the investigational product. Specific details regarding information the site should report for each excursion will be provided to the site. Receipt of materials, door opening and closing, and other routine handling operations where the product(s) are briefly out of labeled temperature range are not considered excursions. More specific details will be provided to the sites separately.

Site staff will instruct subjects on the storage requirements for medications they take home including how to report temperature excursions.

PF-02545920 must not be used outside the context of this protocol. Under no circumstances should the investigator or other site personnel supply PF-02545920 to other investigators, patients, or clinics, or allow supplies to be used other than directed by this protocol, without prior authorization from the sponsor. The investigator must maintain adequate records documenting the receipt, use, loss, or other disposition of investigational product(s). Pfizer may supply drug accountability forms that may be used, or may approve the use of an equivalent form. The form must identify the investigational product, including batch or code numbers, and account for its disposition on a subject by subject basis, including specific dates and quantities. Unused study drug, and unused or used study drug materials must be kept in a secure location for final accountability and reconciliation. At the end of the clinical study, Pfizer will provide instructions as to the disposition of any unused investigational product. The investigator must provide an explanation for any destroyed or missing study drug and/or study drug materials.

